- 1. is the balance of care and choice of provider altered at pilot sites as compared with health authority purchasing (ie will TPPs make greater use of sources of care other than acute hospitals, eg use of alternative therapists; will TPPs adopt different priorities compared with health authorities?)
- 2. what effect does TP have on A&E attendances, emergency admissions, length of inpatient stays, day cases, outpatient referrals, investigations and prescribing?
- 3. to what extent are the activity changes associated with TP also associated with changes in the per patient costs of these services (ie do TPPs manage to make 'savings' in the costs of services)?
- 4. if cost reductions are shown, how are the freed up resources used by TPP sites?
- 5. does TP result in changes in activity by the primary health care team (eg an increase in GPs' availability to patients or access to services such as minor injuries clinics in order to avert hospital utilisation?)?
- 6. how closely do the objectives and business plans of the TPP sites correspond with the changes in activity patterns observed in practice?
- 7. to what extent are the changes in the nature or location of activity purchased by TPP sites a response to the needs, views and /or experiences of patients?
- does TP produce improvements in indicators of the quality of the process of health care (eg outpatient and inpatient waiting times, the speed with which test results and discharge summaries are made available) greater than those in SFH practices?

The fourth objective of the evaluation, and, in many ways the most important in a strategic sense, is to assess the effectiveness of TP through the benefits to patients. Given the timescale of the evaluation (October 1995 - September 1997), prospective data collection will only be possible on a maximum of 12 months before and after TP. The vast majority of TPP sites will only start purchasing in April 1996 with 1995/6 as a preparatory year. In this time, it is likely that any overall changes in patient outcomes will be modest and detecting them would require access to infeasibly

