separate proposal and contract (not included in this proposal). The scope for using routine NHS data to monitor changes in the seven services discussed above is summarised in Table 5.2, which suggests that the routine data, notably the Hospital Episode Statistics (HES) in England, would provide valuable information in relation to three services: emergency admissions, maternity and regional specialties. HES can provide up-to-date data on all inpatient and day case episodes, along with demographic and clinical data. National HES data for 1993/4 along with regional data for 1994/5 and 1995/6 would be used to set baseline levels. Regional data would be used to monitor changes in each of these services. Members of the team have considerable expertise in such analysis at both regional and national level and are confident about being able to negotiate national HES through the National Casemix Office, as has been the case for other projects. (One of the team -[name] - works part time for the National Casemix Office.) Local HES data would be obtained via the TPP site/DHA. Preliminary consultations with Scottish Home and Health Department statisticians indicates that Scottish routine data are highly compatible with English HES and of higher quality. There should be no great difficulty producing an Anglo-Scottish analysis of activity trends. Routine data would have to be supplemented by collection of data at TPP level on use of non-NHS services. This could be obtained from TPP practice software for those sites reporting use of non-NHS services during the fieldwork described in the previous main section.

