Routine data, specifically HES, Community Korner and PACT data, would be of more limited use in the other four services, for which developments in information for contracting might also be expected (see Table 5.2). Both palliative care and mental health, which have growing elements of community and domiciliary care, are only partially captured by routine data, with its emphasis on NHS inpatient activity, leaving gaps regarding community service contacts with patients linked to diseases or to GPs. Although total community health service contacts are recorded, these cannot be linked to specific client groups or patients (the advent of the new computable NHS number will change this - the scope for its use by TPPs will be explored). Data on activity in both community health services and on health promotion are so weak that TPPs may choose to contract on the basis of staff inputs and/or clinics and sessions. For each of these services, routine NHS data would be supplemented by data from each TPP site, depending on how these data are specified by each in their contracting and monitoring arrangements.

Table 5.2
Routine data by topic and adequacy to detect changes in patterns of services

Service	Routine Data	Adequacy
Emergency Admissions	HES/SMR1	OK (all below omit private sector)
Maternity	HES/SMR1	ditto
Regional specialties	HES/SMR1	ditto
Palliative care	HES/SMR1 re NHS inpatients only	missing community service contacts to terminally ill
Mental illness	HES/SMR1 re NHS inpatients only, CPN contacts, PACT	missing community service contacts to mentally ill
Community services	contacts Staff numbers	no linkage to client groups
Health promotion	Clinics Staff numbers	ditto

HES diagnostic data has strict limitations. It is likely that it will only be possible to analyse trends in major diagnostic grouping or by ICD chapters.

Ideally, the analysis of routine data (eg HES/SMR1) would be undertaken for 1993/94, 1994/95, 1995/96 and 1996/97 as soon as possible after the end of March 1997 in order to contribute these analyses to the final report due at the end of September 1997. Unfortunately, there is likely to be a considerable lag in the availability of routine data. It could be October before a complete 1996/97 HES/SMR1 data set is available. Thus, it may not be possible to report on the changes in activity rates before the end of 1997.

Additional data to validate and interpret routine data

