Knowledge of structures and processes followed by particular units is also important because they may affect the way data are recorded. For example, emergency admissions of over 75 year olds may in one unit may go straight to geriatric medicine, and in another unit go first to general medicine followed by transfer to geriatric medicine as a separate FCE. Differences in length of stay and cost of an admission for stroke might be affected by the degree to which that unit included rehabilitation assessment and/or rehabilitation.

Data would also need to be collected on the ways in which other contracts were specified. Routine HES and Korner data offers some scope for monitoring changes in mental health services (HES and PACT) and in palliative care (HES on hospital deaths). For community health services and for health promotion, routine data would appear to have less to offer and contracts may well be specified in terms of staff inputs of blocks of service such as clinic sessions.

The changes in activity recorded in the routine NHS data will be linked to consideration of their costs and, thereby, to an attempt to discover whether TPP sites are more efficient purchasers than health authorities. In order to do so, the work on activity data analysis will be closely co-ordinated with the section which follows on service costs and purchaser efficiency (5.2, below).

5.2: SERVICE COSTS AND PURCHASER EFFICIENCY

Lead: [name], KFPI/LSE

Main comparison: All TPP site service costs versus costs of local health authorities; costs at all

TPP sites before and after introduction of TP; cost comparisons for service packages in 'tracer' studies between TPPs and reference practices (see

section 7)

Research team: [name], [name], KFPI, [name], WIPHM

Introduction

A crucial question for the evaluation will be whether the TPPs are more efficient purchasers than health authorities. More specifically, can they purchase services of a comparable quantity and quality to that of the Health Authority but at a lower total cost; or, equivalently, can they purchase services of higher quality and/or quantity for the same total cost?

This question will be approached in three ways. First, routine data on unit costs will be examined to see whether the TPPs succeed in obtaining lower prices per FCE than HAs. This will give an indication of the ability of TPPs to reduce the cost per unit for services purchased.

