Second, detailed estimates will be constructed of the cost of the services used by the patients who will form the subject of the service-specific sub-studies (the 'tracer' studies -see below, section 7, for details). For the controls, it will be necessary to have data on the volume of services used by each patient and the cost per unit of service.

Finally, the quality of what is purchased by TPPs will be monitored using the various indicators specified in the tracer studies themselves (eg patients'/users' satisfaction in the A and E and community care studies) to see whether any differences in total cost per patient between the pilot sites and controls are associated with differences in the quality indicators (see the second part of 5.2, below).

The detailed development of methods in this part of the evaluation will be informed by discussions with economists in DH/NHSE during early 1996.

SERVICE COSTS AND PURCHASER EFFICIENCY USING ROUTINE ACTIVITY DATA

Specific Objectives

Specific objectives are to compare the costs of TPP site activity with the costs of activity for all other patients in the same districts and to compare TPP site costs before and after the introduction of TP in order to provide answers to the following:

- 1) What are the cost implications of any changes in activity observed in section 5.1, above?
- 2) What are the opportunity cost implications of any changes in activity?
- 3) How do changes in the TPP and comparator DHA Efficiency Indices compare?
- 4) Are there quality changes associated with TPP purchasing that can be ascertained using routine data?
- 5) How will any efficiency improvements achieved by TPP through clinical activity and/or cost changes compare with changes in transactions costs associated with TPPs?

Methods

Objective 1 will be met by linking activity data with unit cost data. The latter will be obtained from DHA Financial Returns for all or main providers (HFR22/TFR2). These will be requested from TPPs and DHAs. Where appropriate, they will be supplemented by data from the service-specific (tracer) studies which are the subject of separate proposals.

Under objective 2, 'opportunity cost' is defined as the value of the alternative activities foregone through actual TPP purchases. It is therefore appropriate to measure this by linking the cost and activity data.

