Objective 3 will be met using data from the previous objectives. To avoid some of the well-known problems with the Efficiency Index, sensitivity analyses will be undertaken, calculating different versions of the index using alternative weighting structures.

Objective 4 will be undertaken using data on mortality, length of stay and destination on discharge. Objective 5 will be undertaken in conjunction with the transactions costs component of the evaluation (see section 6, below) supplemented where possible by other sources.

SERVICE COSTS AND PURCHASER EFFICIENCY FOR SPECIFIC SERVICES

Specific Objectives

The objectives of this part of the evaluation are to:

- determine whether TPPs can purchase specific services (ie maternity services, those for
 people with serious mental illness, and those for people with complex needs for community
 care) of a comparable quantity and quality to that of a health authority, but at a lower total
 cost.
- 2. or, equivalently, to determine whether TPPs can purchase services of higher quality and/or quantity, for the same total cost.

The project will run alongside three components of the evaluation looking at maternity services, community care and services for people with serious mental illness which are the subject of separate but related proposals.

Methods

Estimates will be constructed of the cost of services used by TPP patients and those of reference practices in the service-specific studies. For this purpose, it will be necessary to collect data on the services used by each patient and the cost per unit of service.

For each service-specific study, the project team intend to:

- 1. review the literature on costing methodologies;
- 2. describe possibly pathways of care;
- 3. identify utilisation data for the tracer study team to collect;

- 4. attach costs per unit of utilisation;
- 5. compare costs for actual packages of care using activity data collected by the tracer study team for TPP patients and 'controls';

6. compare costs with outcomes.

Data Requirements

Cost Information

The wide range of direct HPSS costs will be considered in each service-specific study (see separate proposals). Annexe 6 gives examples of some generic services and their estimated costs from PSSRU calculations. Where data are obtained from national routine sources, the usual caveats on quality, accuracy and local context apply. In each case, information will be required on:

- the nature of the service or intervention

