TPPs may wish to contract for **renal services** on the basis of maintenance contracts as some DHAs have done as a means of avoiding the problems associated with contracting on the basis of a mixture of FCEs and outpatient attendances.

As rehabilitation is a service with many more potential clients, a different pattern may emerge. Stroke provides a useful example, in that almost all admissions are emergency, and changes might be expected from TP, with a shift from long stay acute care to rehabilitation whether in hospital, community or at home. Nationally, around 10% of stroke patients stay in acute hospitals for long spells and account for around 60% of inpatient days. These might be expected to be shifted more rapidly either to their homes, with community service backup, or to nursing homes, depending on availability and finance. TPPs may well contract separately for rehabilitation inputs or specify them as part of inpatient stays. Other groups requiring rehabilitation include younger persons who have been seriously injured (such as head injuries). TPPs might spur local strategies to deal with rehabilitation in general.

Genetics is a small but growing services which includes clinical and lab services. Much depends on the advent of new tests which are proliferating. TPPs might be expected to develop overall strategies, perhaps in conjunction with DHAs. Alternatively, TPPs might contract individually on a cost per test basis with laboratories and provide the clinical genetics service, which is largely education and counselling, at TP level.

Palliative care

TP might be expected to lead to more patient-oriented palliative care. A rise in the proportion of deaths occurring at home might be expected given evidence on patients' preferences. A shift might also be expected from costly acute hospital spells to community services, with greater co-ordination of the range of inpatient, community and hospice services.

26 January 1996

Mental illness

TP might be expected to lead to a shift in the balance between drug and inpatient treatment as the costs of the latter become more obvious. Prescriptions of new costly psychiatric drugs such as the SSRIs might be expected to change, relative to both SFH controls and to the baseline year (see below section on prescribing). An increase might be expected in the use of distant NHS beds or private sector beds in emergencies if no NHS beds are available locally.

Community services

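### Objective 4 in section 5.2 reads quality from mortality, length of stay and discharge destination, measures that the protocol expects TP to move by shifting where care is given

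*Protocol*

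**What the plan says.** The routine-data part of section 5.2 of the protocol lists five objectives. The fourth asks: "Are there quality changes associated with TPP purchasing that can be ascertained using routine data". The Methods paragraph fixes the measures: "Objective 4 will be undertaken using data on mortality, length of stay and destination on discharge". It states no favourable direction, time window or definition of mortality.

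The routine source is described in section 5.1: "HES can provide up-to-date data on all inpatient and day case episodes, along with demographic and clinical data". For palliative care, Table 5.2 gives the source as "HES/SMR1 re NHS inpatients only" and notes that community contacts with the terminally ill are missing. The only routine death data named are in the same section, among the sources for monitoring change: "in palliative care (HES on hospital deaths".

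The protocol's predictions for TP are:

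- **Length of stay.** Table 5.1 and Annexe 5 expect it to fall for emergency admissions, especially among long-stay patients.
- **Destination.** Annexe 5 says of long-stay stroke patients: "These might be expected to be shifted more rapidly either to their homes, with community service backup, or to nursing homes".
- **Place of death.** For palliative care, Annexe 5 says: "A rise in the proportion of deaths occurring at home might be expected given evidence on patients' preferences". Table 5.1 expects palliative care to move from acute hospital to community services.
- **Emergency admissions.** Table 5.1 expects the rate to fall.

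**The concern.** Length of stay is a predicted activity effect in section 5.1 and evidence of quality in section 5.2. Discharge destination is in the same position for stroke, and hospital deaths for palliative care. If TP does what the protocol expects, all three measures can change because care has moved, whether quality has risen, fallen or stayed the same. A stay shortened by good community support and one shortened by discharge before the patient was ready look alike in these data.

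This matters because the Introduction to section 5.2 asks whether TP pilots (TPPs) can buy services of comparable quantity and quality at lower total cost. In the routine-data comparison covering all TPP sites, objective 4 is the quality part of that question. A quality measure that moves with the expected cost-saving mechanism cannot test whether quality was held constant.

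**Working it through.** The protocol gives no sample size, power or numerical target for objective 4, so there is no figure to reproduce. The check is a reading of the text plus two illustrations.

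**1. Side by side**

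| Measure under objective 4 | Predicted TP effect | Where predicted |
|---|---|---|
| Length of stay | Falls, long stays most | Table 5.1; Annexe 5, emergency admissions |
| Destination on discharge | Faster to home or nursing home (stroke) | Annexe 5, rehabilitation |
| Mortality (hospital deaths, by inference) | More deaths at home (palliative care) | Annexe 5; Table 5.1 |

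In Study 4 of the mental illness proposal, length of stay and destination on discharge from HES are listed as physical resource use, not quality.

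**2. Length of stay, from the protocol's stroke figures**

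Annexe 5 says that around 10% of stroke patients account for around 60% of inpatient days. Set the overall mean stay to 1.

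- Long-stay patients: 0.60 / 0.10 = 6.0 times the mean.
- All others: 0.40 / 0.90 = 0.44 times the mean.
- Cutting the long stays by a fraction c changes the overall mean by -0.60 × c. For c = 25%, 50% and 75% this is -15%, -30% and -45%.
- Cutting them to the others' average changes it by 0.44 - 1 = -56%.

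Transfer alone is enough to produce these falls.

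**3. Hospital fatality with total deaths unchanged**

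The documents give neither a hospital fatality f nor the size of any shift, so these are assumptions: f = 5%, 10% or 20%; share s of hospital deaths moved home; share q of non-fatal admissions averted.

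- Deaths moved home, patient still admitted: f(1 - s).
- Deaths moved home, patient never admitted: f(1 - s) / (1 - fs).
- Non-fatal admissions averted: f / (1 - q(1 - f)).

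| f | s = 10%: admitted / never admitted | s = 20%: admitted / never admitted | q = 10% | q = 20% |
|---|---|---|---|---|
| 5% | 4.50% / 4.52% | 4.00% / 4.04% | 5.52% | 6.17% |
| 10% | 9.00% / 9.09% | 8.00% / 8.16% | 10.99% | 12.20% |
| 20% | 18.00% / 18.37% | 16.00% / 16.67% | 21.74% | 23.81% |

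Moving deaths home lowers recorded fatality by about 8% to 20% in relative terms. Averting non-fatal admissions raises it by about 9% to 24%. With both at 10% and f = 5%, where the patients who die at home were first admitted: 0.045 / (1 - 0.10 × 0.95) = 0.045 / 0.905 = 4.97%, almost no net change.

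**The case against.** Several points on the other side stand.

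- **Scope.** The Introduction to section 5.2 sets cost differences against indicators from the tracer studies, such as user satisfaction. Those are separate from objective 4, and much of the cost-quality comparison runs through them. A reader might infer that the whole efficiency conclusion rests on the three routine measures; the documents do not support that.
- **Direction.** A reader might also infer that the measures favour TP, or that discharge before a patient is ready would score as better. The protocol states no scoring direction, and the predicted fall in emergency admissions could raise hospital fatality. A bias in favour of TP is not established.
- **Reach of the predictions.** More deaths at home is predicted for palliative care only, and the faster move home or to nursing homes is a stroke example. Neither is stated for emergency admissions in general.
- **Meaning of mortality.** The Methods paragraph does not say in-hospital. That is inferred from the HES/SMR1 source and the reference to hospital deaths.
- **Unused process indicators.** Section 2 gives examples of process quality ("eg outpatient and inpatient waiting times, the speed with which test results and discharge summaries are made available"), but they illustrate the third objective as a whole. Objective 4 is not obliged to use them.
- **Room for refinement.** Section 5.2 says methods will be developed in discussion with departmental economists, and windows or case-mix adjustment may properly sit in an analysis plan not shown here.

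Two apparent safeguards do not answer the point. Section 5.1 asks for routine trends to be read against each TPP's objectives and the provider's processes, with length of stay as its example. That helps to judge whether TP caused a change, not whether the change is better care. Reporting destination beside mortality would reveal some displacement, but would not turn either into a quality measure.

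**Conclusion.** The point holds for objective 4 of the routine-data part of section 5.2, and no further. Mortality (if it means hospital mortality), length of stay and destination are confounded with the predicted shift in place of care and cannot by themselves show a quality change in either direction.

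The effect on length of stay can be large: a 30% lower mean for stroke if the long stays are halved, using the protocol's 10% and 60% figures and an assumed halving. For mortality the sign is indeterminate. The fatality levels and shifts used above are assumptions, and on them recorded fatality can fall, rise or stay level with deaths unchanged. The change is worth making because the measures are named in the protocol and the core of the remedy is cheap.

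**What to change.** In section 5.2, objective 4:

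1. Report length of stay, destination on discharge and hospital deaths (as place of death) as activity measures, and draw no quality conclusion from them alone.
2. Add emergency readmission within a fixed window, from the same HES/SMR1 records after combining finished consultant episodes (FCEs) into admissions. Express it per discharge and show it beside the emergency admission rate. The community care proposal already floats re-admission as a possible routine-data indicator, although only tentatively and in a list that also contains length of stay.
3. Make a mortality claim only if deaths in any place can be counted, within a fixed window of admission or per registered population. Otherwise make none.

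The first change costs only wording. The second needs derivation work: section 5.1 itself warns of multiple FCEs within one admission, and whether admissions of the same patient can be linked should be confirmed early. Readmission is also partly sensitive to TP's incentive to avoid emergency admissions, so it must be read with that caveat. The third depends on a source of deaths outside hospital that the protocol does not name.
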